8.3.7 Serious Adverse Event Reporting

The study clinician will immediately report to the sponsor any serious adverse event, whether or not considered GNB related, including those listed in the protocol or investigator brochure and must include an assessment of whether there is a reasonable possibility that the GNB caused the event. Study endpoints that are serious adverse events (e.g., all-cause mortality) must be reported in accordance with the protocol unless there is evidence suggesting a causal relationship between the GNB and the event (e.g., death from anaphylaxis). In that case, the investigator must immediately report the event to the sponsor.

New information regarding the SAE will be reported as it becomes available and in the same manner that the initial SAE (i.e. SAE form). All serious adverse events (SAEs) will be followed until satisfactory resolution or until the site investigator deems the event to be chronic or the participant is stable. Other supporting documentation of the event may be requested by the Data Coordinating Center (DCC)/study sponsor and should be provided as soon as possible.

8.3.8 Reporting Events to Participants

Any expected adverse events are anticipated to occur within the first 30 minutes of the GNB, such that all participants will be monitored during that time in person. Any concerns of potential adverse events will be communicated to participants at this time.

8.3.9 *Events of Special Interest*

Not applicable.

8.3.10 *Reporting of Pregnancy*

Not applicable.

8.4 *Unanticipated Problems*

8.4.1 *Definition of Unanticipated Problems (UP)*

The Office for Human Research Protections (OHRP) considers unanticipated problems involving risks to participants or others to include, in general, any incident, experience, or outcome that meets all the following criteria:

- Unexpected in terms of nature, severity, or frequency given (a) the research procedures that are described in the protocol-related documents, such as the Institutional Review Board (IRB)-approved research protocol and informed consent document; and (b) the characteristics of the participant population being studied;
- Related or possibly related to participation in the research (“possibly related” means there is a reasonable possibility that the incident, experience, or outcome may have been caused by the procedures involved in the research); and
- Suggests that the research places participants or others at a greater risk of harm (including physical, psychological, economic, or social harm) than was previously known or recognized.

8.4.2 *Unanticipated Problem Reporting*

Unanticipated problems (UPs) such as:

- Post-marketing withdrawal of a drug, device, or biologic used in a research protocol due to safety concerns.
- FDA ban of a drug, device, or biologic used in a research protocol due to safety concerns.
- Complaint of a participant when the complaint indicates unexpected risks, or the complaint cannot be resolved by the research team
- Breach of confidentiality
- Incarceration of a participant when the research was not previously approved under Subpart C and the investigator believes it is in the best interest of the subject to remain on the study
- Premature closure of a study (e.g., due safety, lack of efficacy, feasibility, financial reasons, etc.)

should be reported by the investigator to the medical director. The UP report will include the following information:

- Protocol identifying information: protocol title and number, PI's name, and the IRB project number;
- A detailed description of the event, incident, experience, or outcome;
- An explanation of the basis for determining that the event, incident, experience, or outcome represents an UP;
- A description of any changes to the protocol or other corrective actions that have been taken or are proposed in response to the UP.

To satisfy the requirement for prompt reporting, UPs will be reported using the following timeline:

- UPs that are serious adverse events (SAEs) will be reported as any other SAE.
- Any other UP will be reported to the IRB and to the DCC within 48 hours of the investigator becoming aware of the problem.
- All UPs should be reported to appropriate institutional officials (as required by an institution's written reporting procedures), the supporting agency head (or designee), and the Office for Human Research Protections (OHRP) within 48 hours of the IRB's receipt of the report of the problem from the investigator.

8.4.3 Reporting Unanticipated Problems To Participants

Not applicable.

8.5 Device Reporting

Not applicable.

9 STATISTICAL CONSIDERATIONS

9.1 Statistical Hypotheses

Primary endpoints:

- H_0 : Mean change in pain levels pre / post GNB = Mean change in pain levels pre / post conventional therapy
- H_1 : Mean change in pain levels pre / post GNB \neq Mean change in pain levels pre / post conventional therapy

Secondary endpoints:

- H_0 : Mean duration of analgesia for patients receiving GNB = Mean duration of analgesia for patients receiving conventional therapy
- H_1 : Mean duration of analgesia for patients receiving GNB \neq Mean duration of analgesia for patients receiving conventional therapy
- H_0 : Mean APS-POQ-RED score for patients receiving GNB = Mean APS-POQ-RED score for patients receiving conventional therapy
- H_1 : Mean APS-POQ-RED score for patients receiving GNB \neq Mean APS-POQ-RED score for patients receiving conventional therapy
- H_0 : Mean ED LOS for patients receiving GNB = Mean patient satisfaction for patients receiving conventional therapy
- H_1 : Mean ED LOS for patients receiving GNB \neq Mean patient satisfaction for patients receiving conventional therapy

9.2 Sample Size Determination

To determine the number of patients needed in each study arm for sufficient sample size we considered the primary outcome of change in pain levels pre/post treatment as measured by the NRS as this was the largest sample size needed to detect a clinically meaningful effect.

The sample size was loosely based on an RCT by [Shanahan et al. 2023](#), for which the mean change in the visual analog scale (VAS: 0-10 scale) from baseline at 2 weeks was 3.5 (GNB) and 0.7 (sham injection group). Assuming the mean change in NRS pain score pre/post treatment between the GNB and standard analgesia (difference in difference) will be smaller in a shorter period of time, group sample size of 17 (each group) will achieve 80% power to detect a difference in NRS between treatment arms as small as 1.6, with alpha set at 0.05 and standard deviation of differences set at 2.0 using a two-sided two-sample equal-variance t-test with a 5-10% loss to follow-up at the 24 hour mark.

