Study Population:	
Patients presenting with knee pain at any of the four emergency departments: (1) Hospital of the University of Pennsylvania (HUP), (2) Penn Presbyterian Medical Center (PPMC), (3) Pennsylvania Hospital (PAH), and (4) HUP Cedar (Cedar)
 
All genders, age \geq 18, all demographic groups
 
Moderate to severe knee pain (pain measured on NRS between 5 and 10)
 
Exclusions based on general health status: cognitive impairment / dementia, inability to consent for study procedure
 
Exclusion criteria: pregnant; incarcerated; large knee joint effusion as identified on plain film radiography; acute traumatic etiology for knee pain including fracture, dislocation, or suspected tendonous or ligamentous injury; concern for infection including septic joint, abscess, cellulitis, or sepsis; hemodynamic instability; allergy or contraindication to bupivacaine or any of its components
 
Sample size: 17 patients per treatment arm

Phase:	N/A
Description of Sites/Facilities	
(1) Hospital of the University of Pennsylvania
 
(2) Penn Presbyterian Medical Center
 
(3) Pennsylvania Hospital
 
(4) HUP Cedar

Enrolling Sites:	EDs of the four previously mentioned sites
Description of Study Intervention:	The study intervention is an ultrasound-guided three-point GNB, which involves injection of local anesthetic with adjuvant (ideal bodyweight-dosed bupivacaine 0.5% and dexamethasone 4 mg) around the genicular nerves of the knee. The genicular nerves are a series of four terminal

sensory nerve branches of the femoral nerve that provide sensory innervation to the joint capsule of the knee, thereby providing pain relief without motor blockade or paralysis. See detailed description of the study intervention in Section 6. The comparison control arm involves conventional analgesia for knee pain, which includes oral, intravenous, or topical analgesics (e.g., acetaminophen, non-steroidal anti-inflammatory drugs [NSAIDs], opioids, lidocaine patches, heating or cold packs) and will be determined at the discretion of the primary provider caring for the patient. See detailed description of study control arm in Section 6.

Study Duration: 12-months

[figure not shown]
Participant Duration: 24 to 36-hours

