5.5 Strategies for Recruitment and Retention

Patients presenting to the EDs of HUP, PPMC, PAH, or HUP Cedar with knee pain for whom plain film imaging has been obtained will be screened by a member of study team to determine eligibility based on inclusion and exclusion criteria described in sections 5.1 and 5.2. If the patient is eligible, a member of study team will approach the patient to obtain informed consent.

- Target sample size: 17 patients in both the intervention and control treatment arms
- Anticipated accrual rate: 100%
- Anticipated number of sites and in which participants are to be enrolled: 4 clinical sites (EDs of HUP, PPMC, PAH, or HUP Cedar)
- Source of participants: ED patients
- Recruitment venues: ED
- How potential participants will be identified and approached: (1) Potentially eligible patients under the care of a participating physician will be identified and approached

during the usual course of care. (2) Potentially eligible patients who are not under the direct care of a participating physician will be identified by chart screening and direct communication with the primary physician by either participating physicians or research assistants.

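### The 80% power claim is wrong on its own inputs: 17 per arm gives about 62% power for a 1.6-point difference with SD 2.0, and 80% power only for about 2.0 points.

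*Protocol*

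**What the plan says.** Protocol section 9.2 (Sample Size Determination) sizes the trial on the primary outcome, the pre-to-post change in NRS pain compared between arms. It states that a "group sample size of 17 (each group) will achieve 80% power to detect a difference in NRS between treatment arms as small as 1.6". The remaining inputs are a significance level of 0.05 and, in the protocol's words, a "standard deviation of differences set at 2.0 using a two-sided two-sample equal-variance t-test". The same sentence adds a 5-10% loss to follow-up at 24 hours.

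The figure of 17 is carried unchanged into the synopsis (section 1.1: "Sample size: 17 patients per treatment arm") and the recruitment section (section 5.5: "Target sample size: 17 patients in both the intervention and control treatment arms"). No other standard deviation, target difference or power calculation appears in the protocol.

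**The concern.** All the quantities needed for a two-sample power calculation stand in one sentence, so the claim can be checked without outside information. A standardised difference of 0.8 ordinarily needs about 25 patients per arm for 80% power, so 17 looks too small.

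This calculation is the protocol's only justification for the size of the trial. If the power is overstated, a null result would be read as evidence against a 1.6-point benefit from a trial believed to miss such a benefit one time in five. The real miss rate would be nearly twice that.

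**Working it through.** **Inputs, all from section 9.2**
- n = 17 per arm
- difference between arms in mean change, δ = 1.6
- SD of each patient's pre/post change, σ = 2.0
- α = 0.05, two-sided (section 9.4.1 also makes all tests two-sided)
- two-sample equal-variance t-test
- stated power 80%

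**1. Power with the stated inputs**

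Standardised difference: d = δ/σ = 1.6/2.0 = 0.8.

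Noncentrality: d × √(n/2) = 0.8 × √8.5 = 2.332, with 2 × 17 − 2 = 32 degrees of freedom and critical value t = 2.037.

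Power from the noncentral t distribution is **0.619**. A simulation with 200,000 replicates also gave 0.619. The normal approximation is Φ(2.332 − 1.960) = Φ(0.372) = 0.645. The stated 0.80 is not reproduced; it is about 18 percentage points too high.

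**2. Sample size needed for 80% power at δ = 1.6, σ = 2.0**

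Normal approximation: n = 2 × (1.960 + 0.842)² / 0.8² = 2 × 7.85 / 0.64 = 24.5, so 25.

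Noncentral t: 25.5, so **26 per arm**. Power is 0.791 at 25 per arm and 0.807 at 26.

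**3. What 17 per arm can detect**

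The standardised difference with 80% power at 17 per arm is 0.991.
- With σ = 2.0, the detectable difference is 0.991 × 2.0 = **1.98 points**. Power for exactly 2.0 points is 0.807.
- With δ held at 1.6, the SD would have to be 1.6/0.991 = **1.61**.

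**4. Other readings tried**

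| Reading | Result |
|---|---|
| One-sided α = 0.05, n = 17 | power 0.738; needs 21 per arm |
| Two-sample, δ = 2.0, σ = 2.0 | needs 16.7, so 17 per arm, with no allowance for loss |
| One-sample or paired formula, 1.6/2.0 | needs 14.3, so 15; 15/0.9 = 16.7, so 17 |

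The last two rows arrive at 17, but neither matches the text. The first of them uses a different target difference. The second uses a formula that does not compare two arms. Which route was taken, if either, cannot be told from the protocol.

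**5. Loss of patients**

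No allowance is visible: 17 is both the size said to give the power and the enrolment target. The stated loss is at the 24-hour call, whereas the primary score is taken at 1 hour or discharge, so 61.9% is the figure for the primary endpoint. As an assumption only, if one or two patients per arm had no post-treatment score:

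| n per arm | Power for 1.6 | Difference detectable with 80% power |
|---|---|---|
| 17 | 0.619 | 1.98 |
| 16 | 0.591 | 2.05 |
| 15 | 0.562 | 2.12 |

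**The case against.** The best defence is that 2.0 is the SD of a single NRS score and not of the change. The SD of change would then be 2.0 × √(2(1 − ρ)), where ρ is the pre/post correlation, and power would be 0.48 at ρ = 0.3, 0.619 at ρ = 0.5 and 0.83 at ρ = 0.7. A correlation near 0.68 would bring it to about 80%. But the text says "standard deviation of differences set at 2.0", directly after describing the pre/post change as a difference in differences, and no correlation is stated anywhere. This reading does not rescue the claim.

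A second defence is that the planned analysis is more efficient than a t-test. Section 9.4.1 plans a repeated-measures ANOVA with two time points. Its arm-by-time test is the t-test on change, so nothing is gained. A baseline-adjusted model could gain power, but none is planned. With the SD of change at 2.0 it would reach 80% only for a correlation of about 0.3 or lower.

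Third, the true effect may exceed 1.6. The earlier trial cited in section 9.2 showed changes of 3.5 and 0.7, a difference of 2.8. That may be so, but the protocol itself expects a smaller effect over the shorter period and names 1.6 as the smallest difference it can detect.

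Two limits do stand. The figures for 16 and 15 per arm are a scenario, since the protocol states no loss of 1-hour scores. And the calculation shows what 17 per arm can detect, not what the authors meant to detect; any one of the sample size, the difference, the SD or the method could be the wrong entry.

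**Conclusion.** The power statement is wrong as written. Taking 2.0 as the SD of the pre/post change, with the two-sided two-sample t-test at 0.05 that the protocol names, 17 per arm has 61.9% power for 1.6 points, not 80%. The chance of missing a true difference of exactly 1.6 is 38.1%. The difference detectable with 80% power is 1.98 points. No other section corrects the figure, and neither the planned analysis nor a one-sided test reproduces it. Because the primary power claim is about 18 percentage points too high on its own inputs, it must be corrected.

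**What to change.** Keep 17 per arm and rewrite section 9.2 to say that, with an SD of change of 2.0 and a two-sided alpha of 0.05, 17 per arm gives 80% power for a between-arm difference of 2.0 points and about 62% power for 1.6 points. If an SD near 1.6 was intended, state that SD and justify it instead. Move the 5-10% loss statement to the duration-of-analgesia endpoint, which is the one collected at the 24 to 36-hour call.

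This costs a change of wording in one section and a less favourable stated power; no patients are added. If the sponsor wishes to keep 80% power for 1.6 points with an SD of 2.0, wording alone will not do: that needs 26 per arm (52 in total), and sections 1.1 and 5.5 would have to change with it.

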9.3 Populations for Analyses

All patients who are enrolled and receive either the GNB or conventional analgesia as part of the study will be included in the analysis dataset.

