4 STUDY PLAN

4.1 Study Design

This is a prospective, open-label, investigator-initiated, convenience-enrollment, randomized-controlled trial comparing the efficacy of the ultrasound-guided three-point GNB versus conventional analgesia of atraumatic knee pain. Patients who present to the ED with atraumatic knee pain will receive plain film radiography of the knee to evaluate for acute fracture or large knee joint effusion. Patients without radiographic evidence of fracture or large knee joint effusion will be eligible for enrollment. Patients for whom there are concerns for infection, including cellulitis or septic arthritis will be excluded. Other exclusion criteria are listed in Section 5.2. We hypothesize that patients who receive a GNB will experience a greater reduction in pain and longer acting analgesia compared to those managed with conventional analgesia.

Patients who present to one of the four primary ED sites within the Penn Medicine health system (HUP, PPMC, PAH, HUP Cedar) will be eligible for inclusion as participants. Research assistants (RAs), who are present in the ED at HUP and PPMC daily, will assist with recruitment at those sites, and potentially eligible patients at PAH and HUP Cedar will be recruited by participating physicians. The study team will review inclusion and exclusion criteria with the RAs prior to the initiation of patient enrollment. Furthermore, an EPIC Haiku notification will be created to alert the study team of any patient who presents to the ED with knee pain. Prior to recruitment, it is assumed that most patients who will become participants will have been offered conventional oral, intravenous, or topical analgesics as part of their normal treatment regimen. If completion and radiologist read of plain film imaging (1) does not show evidence of acute fracture and (2) does not show evidence of a large knee joint effusion, patients will be screened for eligibility by either an RA or the performing physician. Patients with small or moderate sized effusions will be eligible for inclusion if there is no clinical concern for septic arthritis of the knee. Large effusions will be excluded as this may distort the anatomical and sonographic landmarks for performing the GNB. The physician who performs the GNB for participants may not necessarily be the physician who is primarily caring for the patient clinically in the ED.

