4.4 End of Study Definition

A participant will have completed this study at 24 to 36 hours after blockade, when the research assistant or performing physician will contact the patient via telephone for follow-up assessment, to evaluate for duration of analgesia. For patients that experience an adverse event that requires admission to the hospital or ambulatory follow-up, their participation in the study might be extended beyond 24 to 36-hours as these adverse events and outcomes will be tracked.

Patients who receive the GNB and rate their pain on the NRS before and after the procedure, even those who refuse the APS-POQ-RED survey responses and who are not available to be reached by phone the next day, will still be included in the data analysis for the primary and one secondary endpoint (pain levels, LOS).

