7.3 Lost To Follow-Up

A participant will be considered lost to follow-up if he or she does not respond via telephone at the 24-hour follow-up after three attempts by the participating emergency physician or clinical research assistant. However, patient intervention and any outcome data that has previously been obtained (e.g., data collected at time of discharge from the ED) will still be included. All participants who complete the initial assessment by the time of discharge will be included in the analysis. No follow-up visits will be required.

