8 STUDY ASSESSMENT AND PROCEDURES

8.1 Efficacy Assessments

Patients presenting to the ED of one of the four study locations (HUP, PPMC, PAH, HUP Cedar) with knee pain attributed to knee OA with plain film radiography who are eligible for enrollment based on the inclusion and exclusion criteria described in sections 5.1 and 5.2 will be approached by a member of the study team to obtain informed consent.

Prior to randomization, a pain score will be obtained using the NRS by the performing physician. Patients will be randomized to either the intervention arm (GNB) or the control arm, at which point they will receive treatment. At either 1-hour after enrollment or at time of discharge from the ED (whichever occurs first), the performing ED physician, or research assistant will ask the patient to rate their pain severity on the NRS. At that same time, a member of the study team will also have the patient complete the APS-POQ-RED. At 24 to 36-hours after treatment, a clinical research assistant or the treating emergency physician will contact the patient to obtain follow-up assessment and duration of analgesia.

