9.4 Statistical Analyses

9.4.1 General Approach

Prior to analysis, all primary and secondary outcome measures will be summarized with descriptive statistics (mean \pm standard deviation (SD) or median and IQR), their distributions examined, tested for normality and transformed using log base 10 as needed. Additionally, all

demographics will be summarized using mean \pm SD or median and IQR, for continuous variables and frequencies and percentages for categorical variables. Results from statistical testing for continuous variables, will be presented with p-values and 95% confidence intervals for tests using means or medians and IQR if a non-parametric test is used. For categorical variables, the chi-square or Fisher's exact test will be performed to examine whether treatment arms differ with regard to demographics and other baseline variables. Similarly, for side effects, descriptive statistics and Fisher's exact tests will be performed for possible differences between the treatment arms. Regardless of type statistical test, all will be two-sided.

The primary efficacy endpoint is change in pain level as measured on the NRS at baseline (pre intervention) and at post intervention (either 1-hour post-enrollment or at time of ED discharge, whichever occurs first) in both treatment arms. The NRS is an ordinal variable, measured on a 0-10 scale and will be treated as a repeated measure. To determine differences in pain level between GNB and conventional analgesia treatment arms, a 2-factor analysis of variance in repeated measures will be performed where treatment arm is the grouping factor and time (pre/post) is the repeated measure. To adjust for multiple comparisons, post-hoc pairwise Tukey-Kramer tests will be performed. Results will be presented as means \pm 95% confidence intervals for each treatment arm/time point. Shapiro-Wilkes test will be used to test for normality. If not normally distributed, data will be transformed using log base 10 transformation. If missing time points, analysis type will change to a mixed general linear model where treatment arm is a fixed factor and time is random.

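### Section 9.3 makes treatment received after randomisation a condition of analysis, 7.3 and 4.4 word inclusion differently, and no section secures analysis by assigned arm

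*Protocol*

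**What the plan says.** Four parts of the protocol bear on who is analysed.

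- Section 9.3, the only section that defines an analysis population, takes in "All patients who are enrolled and receive either the GNB or conventional analgesia as part of the study".
- Section 7.3, on patients lost to the telephone follow-up: "All participants who complete the initial assessment by the time of discharge will be included in the analysis".
- Section 4.4 says that "Patients who receive the GNB and rate their pain on the NRS before and after the procedure" stay in the analyses of pain and ED length of stay even if they refuse the questionnaire or miss the call. It has no matching sentence for controls.
- Section 9.4.1, on the primary endpoint: "If missing time points, analysis type will change to a mixed general linear model". The main analysis is a repeated-measures analysis of variance in which "treatment arm is the grouping factor and time (pre/post) is the repeated measure".

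Section 8.1 fixes the sequence: "Patients will be randomized to either the intervention arm (GNB) or the control arm, at which point they will receive treatment". Section 6.3 states that participants, performing physicians and research assistants are all unblinded. Section 7.2 allows withdrawal at any time. Section 4.1 assumes that, before recruitment, "most patients who will become participants will have been offered conventional oral, intravenous, or topical analgesics".

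Intention-to-treat appears in the abbreviation list and nowhere else. The secondary hypotheses in 9.1 are phrased by the treatment patients receive.

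**The concern.** Randomisation protects the comparison only if membership of the analysis set does not depend on what happens afterwards. Under 9.3 it does: a patient who is randomised, scored and then given neither a block nor a conventional analgesic within the study falls outside the dataset. This could happen through withdrawal before treatment, a block that is not performed, or a control who was medicated before enrolment and is given nothing further. The qualifier about treatment being part of the study bears more on controls, because a block is always a study act while conventional analgesia may precede enrolment.

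In an open-label trial, who ends up untreated can depend on the arm. Sections 9.3 and 7.3 also give different answers for the same patient, and 9.4.5 plans a look at the endpoints after 30 patients. The choice between the rules could therefore be made by people who have seen results. With 17 patients per arm, each exclusion carries weight.

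**Working it through.** The plan gives no figure for untreated patients, so there is none to reproduce. The check has two parts: a comparison of the rules, then a sensitivity calculation on stated assumptions.

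**The rules applied to the same patients**

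| Randomised patient | 9.3 | 7.3 | 4.4 |
|---|---|---|---|
| Either arm, both NRS scores, neither treatment received | Out | In | Silent |
| Assigned block, not done, conventional analgesia given, both scores | In | In | Silent |
| Control, treated, both scores, telephone call missed | In | In | Silent |
| Block received, both scores, telephone call missed | In | In | In |
| Either arm, treated, no post score | In | Depends on the meaning of initial assessment | Silent |

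The first row is the direct contradiction: 9.3 excludes a patient whom 7.3 includes. The third and fourth rows show that 4.4 covers one arm only. In the last row, 9.4.1 keeps the patient through the mixed model. In the second row the patient is in the dataset, and no sentence says in so many words which arm the patient counts in.

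**Possible size**

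Inputs from section 9.2: 17 per arm, target difference 1.6 NRS points, standard deviation 2.0. Assumptions, not in the protocol: m patients are dropped from one arm only, and their mean change differs by g = 2 points from that of the patients kept.

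The full-arm mean is (1 − m/17) × kept mean + (m/17) × dropped mean. The kept mean therefore differs from the full-arm mean by (m/17) × g.

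- One patient is 1/17 = 5.9% of an arm.
- m = 1: 1/17 × 2 = 0.12 points, 7% of 1.6.
- m = 2: 2/17 × 2 = 0.24 points, 15% of 1.6.
- m = 3: 3/17 × 2 = 0.35 points, 22% of 1.6.
- m = 0: no shift.

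For scale, the standard error of the difference on the protocol's inputs is 2.0 × √(1/17 + 1/17) = 0.69. The largest shift above is about half of that (0.35/0.69 = 0.51). The sign depends on which arm loses patients and whether they did better or worse than those kept; the protocol settles neither.

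**The case against.** The strongest reply is that the plan already comes close to a randomised comparison, and most of it stands.

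- A reader might infer that the primary comparison is not the randomised one. The text does not show that. Section 9.4.1 groups by treatment arm, and 4.1, 6.3 and 8.1 use arm for the assignment. Section 9.3 accepts either treatment, so a patient assigned to the block who gets only tablets stays in. Nothing says that patients are regrouped by what they received.
- A reader might infer that dropped controls would be those whose earlier analgesic was working, so that the rule favours the block. The text does not support this either. Section 5.1 requires NRS 5 to 10, and 4.1 takes the rating as current pain whatever was given before, so every patient enters with moderate to severe pain. Sections 4.1 and 6.1.1 say that controls will be treated, 6.4 makes this part of adherence, and the synopsis counts even hot or cold packs. An untreated control would be a departure from the plan, and there may be none.
- Section 4.4 might be read as excluding controls, or as conflicting with the mixed model because it mentions both scores. It says who is still included, not who is excluded. It is a sufficient condition with one-sided wording.
- Section 7.3 concerns missed telephone calls, and its initial assessment may mean the whole ED assessment.
- The unused abbreviation proves little, since the list holds other unused entries.

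What remains: 9.3 conditions on receipt of treatment, 7.3 does not, and analysis by assignment is left to inference from the word arm. A separate analysis plan could add detail, but the two protocol sections would still disagree.

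**Conclusion.** The point holds in a limited form. The protocol does not secure the primary comparison as the randomised one. Randomised patients who receive neither treatment can be removed under 9.3, possibly more in one arm than the other, while 7.3 would keep those who were assessed. That the rules disagree is certain from the text. Whether any patient would be affected is not.

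The direction of any bias is unknown, and its size may be zero. The shift of 0.12 to 0.35 NRS points rests on two assumptions without support in the protocol: 1 to 3 of 17 patients lost from one arm, and a 2-point difference between those lost and those kept. It shows that a few exclusions could matter at this sample size; it does not estimate what will happen. The wording should be corrected before any outcome data are examined.

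**What to change.** - Section 9.3: define the primary analysis set as all randomised patients, analysed in the arm assigned, whatever treatment they receive.
- Section 4.4: reword the retention statement to cover both arms.
- Section 7.3: refer to the 9.3 definition, and say what the initial assessment is.
- Missing post scores: state that such patients stay in the primary analysis through the model already named in 9.4.1.
- Keep a set defined by treatment received for a sensitivity analysis only.

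The cost is protocol wording; neither the planned sample size nor patient care changes. The downside is slight dilution if some assigned blocks are not done. If the true difference is 1.6 and 1 to 3 of 17 patients assigned to the block respond as controls do, the expected difference falls to 1.6 × 16/17 = 1.51, or at most to 1.6 × 14/17 = 1.32. Part of this is already implicit, because 9.3 keeps such patients when they receive conventional analgesia.
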